## **5.3 Lifestyle Considerations**

Participants discharged from the hospital must follow the contraception requirements outlined in Appendix F.

Restrictions relating to concomitant medications are described in Section 6.5.

## **5.4 Screen Failures**

Screen failures are defined as participants who consent to participate in the clinical study but are not subsequently entered in the study. A minimal set of screen failure information is required to ensure transparent reporting of screen failure participants to meet the Consolidated Standards of Reporting Trials publishing requirements and to respond to queries from regulatory authorities. Minimal information includes demography, screen failure details, eligibility criteria, and any SAE unrelated to the disease under investigation.

Individuals who do not meet the criteria for participation in this study (screen failure) may be rescreened. Rescreened participants should be assigned the same participant number as for the initial screening.

## 6 STUDY INTERVENTION

Study intervention is defined as any investigational intervention(s), marketed product(s), placebo, or medical device(s) intended to be administered to a study participant according to the study protocol.

### 6.1 Study Intervention(s) Administered

#### 6.1.1 Investigational Medicinal Products

Details of the investigational medicinal products are provided in Table 5.

**Table 5 Investigational Medicinal Products**

Intervention Name	Acalabrutinib	Acalabrutinib
Type	Drug	Drug
Formulation	Suspension extemporaneously constituted from acalabrutinib capsules and 100 mL flat COCA-COLA (see Handling Instructions)	Capsule a
Strength/concentration	100 mg/100 mL	100 mg
Dosage level	100 mg	100 mg
Route of administration	Nasogastric	Oral
Regimen	bid (multiple dose)	bid (multiple dose)
Use	Experimental	Experimental
Sourcing	Sponsor (AstraZeneca) b	Sponsor (AstraZeneca)
Former name/alias	ACP-196	ACP-196

a Acalabrutinib capsules will only be taken orally if a participant is no longer intubated and can swallow pills during the treatment period.

b Note: COCA-COLA will be supplied locally.  
bid = twice daily.

The COCA-COLA needed to constitute the acalabrutinib suspension will be supplied locally and must meet the criteria below:

- COCA-COLA original (minimum 250 mL countenance, bottles with caps). If cans are used instead, 200 to 500 mL bottles with caps are needed to degas the soda to avoid foaming. A volume of 100 mL of flat COCA-COLA is needed for the preparation of the 100 mg acalabrutinib suspension.
- Hard plastic or glass bottles of 200 to 500 mL capacity with screw caps to constitute the suspensions; preferably amber glass.

## **6.1.2 Dosing Instructions and Duration**

### **6.1.2.1 Dosing and Duration of Treatment**

Treatment with acalabrutinib suspension (ie, acalabrutinib 100 mg suspension in COCA-COLA delivered via NG tube) will be initiated on Day 1. All participants must have received PPI treatment for  $\geq 24$  hours prior to the first dose of acalabrutinib suspension. All participants will receive acalabrutinib suspension bid, approximately 12 hours apart, for 14 days (a maximum of 28 doses). The acalabrutinib suspension must be prepared according to the Handling Instructions. **NOTE:** COCA-COLA contains glucose (5 g per 100 mL). Blood glucose levels of diabetic participants must be monitored as clinically indicated and blood glucose-lowering medications adjusted accordingly.

Administration of acalabrutinib suspension should not occur within a 2-hour window before or after feeding or delivery of other drugs. Nasogastric tubing should be flushed with water prior to and after acalabrutinib suspension delivery according to the Handling Instructions.

### **6.1.2.2 Dosing of Participants Who are no Longer Intubated**

If a participant is no longer intubated and can swallow pills during the treatment period, the participant should continue taking acalabrutinib 100 mg capsules orally bid. Capsules should be swallowed intact. Acalabrutinib can be taken with or without food.

- If a participant remains on a PPI and switches to taking capsules orally, 100 mg acalabrutinib capsules should be dosed orally with at least 100 mL of COCA-COLA.
- If a participant is no longer taking a PPI and switches to taking capsules orally, acalabrutinib capsules should be taken with water.

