### Overall Design

This is an open-label, multi-dose study to evaluate the PK, and safety and tolerability of acalabrutinib suspension, when coadministered with a PPI, in participants with confirmed SARS-CoV-2 infection requiring hospitalization due to respiratory failure (as defined in the table above) attributable to COVID-19 pneumonia and who have an NG tube in place. Approximately 20 participants will be included to ensure at least 16 participants are evaluable. Participants are considered evaluable if they have an evaluable PK profile, ie: (1) complete PK Visit 2 assessments; (2) receive active treatment; and (3) do not have unavailable or

incomplete data that may influence the PK analysis.

In addition to receiving BSC, participants will receive acalabrutinib suspension (ie, acalabrutinib 100 mg suspension in COCA-COLA® delivered via NG tube) bid for 14 days (a maximum of 28 doses). Best supportive care is per discretion of the Investigator and institutional guidelines. Standard NG tubes supplied by the hospital will be used. Nasogastric tube placement in the stomach will be confirmed by chest x-ray.

To assess the effect of PPIs, all participants must be receiving treatment with a PPI at the start of the study. Treatment with a PPI can begin at any time prior to enrollment, provided participants have received PPI treatment for at least 24 hours prior to the first dose of acalabrutinib suspension. Any PPI is permitted, provided it meets the minimum equivalent daily dose of 20 mg rabeprazole. Participants must be on this dosage of PPI at the start of the study. They may be weaned off PPIs during the study if medically appropriate.

Blood samples for plasma PK assessment of acalabrutinib and its metabolite (ACP-5862) will be collected at pre-dose and 0.5, 1, 2, 4, 6, and 12 hours following treatment with acalabrutinib suspension as described in the table below. Note that the sample at 12 hours must be collected prior to the subsequent acalabrutinib dose (for trough PK sample).

PK Visit	Description	Rationale
PK Visit 1	First PK sampling will occur on Day 1 (ie, first dosing day for acalabrutinib suspension)	Allows an early assessment of acalabrutinib and ACP-5862 PK in participants receiving acalabrutinib suspension via NG tube

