**Figure 1 Study Design**

Scenarios of PK visits relative to PPI start	PPI Dosing Starts (≥24 h prior to first acalabrutinib dose)	PK Visit 1 a (coincides with Day 1 of study)	PK Visit 2 a (≥4 d after start of PPI and any time after 2 doses of acalabrutinib)	PK Visit 3 a (3 days after PK Visit 2 or on last day of acalabrutinib treatment)
Scenario 1 (shown in figure)	Day -1	Prior to first acalabrutinib dose	Day 3 (prior to fifth dose)	Day 6 (prior to 11th dose)
Scenario 2	Day -2	Prior to first acalabrutinib dose	Day 2 (prior to third dose)	Day 5 (prior to ninth dose)
Scenario 3	Day -3	Prior to first acalabrutinib dose	Day 2 (prior to third dose)	Day 5 (prior to ninth dose)
Scenario 4	Day -4 or earlier	Prior to first acalabrutinib dose	Day 2 (prior to third dose)	Day 5 (prior to ninth dose)

a Blood samples for plasma PK assessment of acalabrutinib and its metabolite (ACP-5862) will be collected at pre-dose and 0.5, 1, 2, 4, 6, and 12 hours following treatment with acalabrutinib suspension. Note that the sample at 12 hours must be collected prior to the subsequent acalabrutinib dose (for trough PK sample).

Note: PK Visit 2 can occur as early as Day 2 (if participant has been on a PPI for ≥ 4 consecutive days prior to receiving the third acalabrutinib dose), and up to Day 4 (if participant initiated PPI treatment 24 hours prior to receiving the first dose of acalabrutinib on Day 1). See Table 4 for more information.

bid = twice daily; PK = pharmacokinetic(s); PPI = proton-pump inhibitor.

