## 4 STUDY DESIGN

### 4.1 Overall Design

This is an open-label, multi-dose study to evaluate the PK, and safety and tolerability of acalabrutinib suspension, when coadministered with a PPI, in participants with confirmed SARS-CoV-2 infection requiring hospitalization due to respiratory failure (as defined in Section 8.1.1.1) attributable to COVID-19 pneumonia and who have an NG tube in place. Approximately 20 participants will be included to ensure at least 16 participants are evaluable. Participants are considered evaluable if they have an evaluable PK profile, ie: (1) complete PK Visit 2 assessments; (2) receive active treatment; and (3) do not have unavailable or incomplete data that may influence the PK analysis.

In addition to BSC, participants will receive acalabrutinib suspension (ie, acalabrutinib 100 mg suspension in COCA-COLA delivered via NG tube) bid for 14 days (a maximum of 28 doses). Best supportive care is per discretion of the Investigator and institutional guidelines. Standard NG tubes supplied by the hospital will be used. Nasogastric tube placement in the stomach will be confirmed by chest x-ray.

To assess the effect of PPIs, all participants must be receiving treatment with a PPI at the start of the study. Treatment with a PPI can begin at any time prior to enrollment, provided participants have received PPI treatment for at least 24 hours prior to the first dose of acalabrutinib suspension (Figure 1). Any PPI is permitted, provided it meets the minimum equivalent daily dose of 20 mg rabeprazole (Appendix H). Participants must be on this dosage

of PPI at the start of the study. They may be weaned off PPIs during the study if medically appropriate.

Blood samples for plasma PK assessment of acalabrutinib and its metabolite (ACP-5862) will be collected at pre-dose and 0.5, 1, 2, 4, 6, and 12 hours following treatment with acalabrutinib suspension as described in Table 4 below and illustrated in Figure 1. Note that the sample at 12 hours must be collected prior to the subsequent acalabrutinib dose (for trough PK sample).

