**Table 4 Pharmacokinetic Sampling Relative to Start of Proton-pump Inhibitor Treatment**

PK Visit	Description	Rationale
PK Visit 1	First PK sampling will occur on Day 1 (ie, first dosing day for acalabrutinib suspension)	Allows an early assessment of acalabrutinib and ACP-5862 PK in participants receiving acalabrutinib suspension via NG tube
PK Visit 2	Second PK sampling will occur a minimum of 4 days after the start of PPI treatment, irrespective of the timing of NG tube placement and any time after 2 doses of acalabrutinib suspension have been given (ie, PK sampling can begin prior to the third dose, or anytime thereafter) PK Visit 2 can occur as early as Day 2 (if participant has been on a PPI for $\geq 4$ consecutive days prior to receiving the third acalabrutinib dose), and up to Day 4 (if participant initiated PPI treatment 24 hours prior to receiving the first dose of acalabrutinib on Day 1)	PPI exposure must occur for 4 consecutive days to reach the maximum PPI on-target effect PK sample can commence at any point after the second dose of acalabrutinib suspension to ensure steady-state levels of the active metabolite and maximal [REDACTED] [REDACTED] [REDACTED] has been reached
PK Visit 3	Third PK sampling will occur 3 days after PK Visit 2, OR on the last day the participant receives acalabrutinib treatment, whichever comes first	Allows an additional opportunity to assess the steady state PK of acalabrutinib and ACP-5862 PK following delivery of acalabrutinib suspension via NG tube

[REDACTED] NG = nasogastric; PK = pharmacokinetic(s); PPI = proton-pump inhibitor.

Safety assessments, including AE reporting, will be performed through 28 ( $\pm 3$ ) days after the last dose of the acalabrutinib suspension.

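### Section 6.1.2.2 moves an extubated participant who can swallow to capsules even when the gastric tube is still in place and PK Visit 2 is pending, which forfeits the suspension profile the primary objective needs

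*Protocol*

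**What the plan says.** Section 6.1.2.2 gives the switch instruction: "If a participant is no longer intubated and can swallow pills during the treatment period, the participant should continue taking acalabrutinib 100 mg capsules", by mouth and twice daily. Table 5, footnote a, uses the same two conditions, but as a limit on capsule use rather than an order to switch: "Acalabrutinib capsules will only be taken orally if a participant is no longer intubated and can swallow pills during the treatment period". Neither place mentions the tube or PK Visit 2.

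Section 4.1 calls a participant evaluable on three items: "complete PK Visit 2 assessments; (2) receive active treatment; and (3) do not have unavailable or incomplete data that may influence the PK analysis". The synopsis has the same three. Section 4.1 also says the PK samples are "collected at pre-dose and 0.5, 1, 2, 4, 6, and 12 hours following treatment with acalabrutinib suspension". Table 4 allows PK Visit 2 "any time after 2 doses of acalabrutinib suspension have been given", once PPI treatment has run for four days. It places the visit between Day 2 and Day 4, depending on when the PPI was started.

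The primary PK objective in Section 3 concerns the suspension given with a PPI. Section 9.2 plans about 20 enrolled for at least 16 evaluable.

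**The concern.** PK Visit 2 is the profile on which evaluability rests, and Section 4.1 expects it to follow a suspension dose. The switch rule can take effect first. When it does, nothing in the protocol keeps the participant on suspension until the profile is complete or returns them to it for that dose. Section 8.2.5.2 tells sites not to miss PK samples but is silent on the formulation of the sampled dose.

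A site that follows every instruction can thus give up a primary profile it could have collected. The SAP cannot repair this. It can set a capsule profile aside, but it cannot recover a suspension dose that was never given.

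**Working it through.** **1. The plan's own count.** 16 × 1.25 = 20, which reproduces the figure in Section 9.2. The gap is 20 − 16 = 4 places. One forfeited profile uses 1 of those 4 and is 1/16 = 6.25% of the minimum evaluable set.

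**2. When the sampled dose falls.** With twice-daily dosing, Day d holds doses 2d − 1 and 2d, and its first dose comes 24 × (d − 1) hours after the first dose of the study.

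| PK Visit 2 | Sampled dose | Hours after first dose |
|---|---|---|
| Day 2 | 3rd | 24 |
| Day 3 | 5th | 48 |
| Day 4 | 7th | 72 |

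Figure 1 confirms the third dose for Day 2 and gives "Day 3 (prior to fifth dose" in Scenario 1. Day 4 comes from Table 4.

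**3. The rules set side by side for a switch before the sampled dose.**
- Switch after dose 1: the two suspension doses required by Table 4 can no longer be reached.
- Switch after dose 2 or later: the Table 4 condition is met, but the dose given at PK Visit 2 is a capsule, so the samples do not follow suspension as Section 4.1 requires.

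Either way there is no suspension profile at PK Visit 2.

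**4. Would the tube still be there?** Inclusion criterion 5 requires a tube expected to stay at least 3 days after enrollment, and it accepts percutaneous tubes, which need not come out at extubation. I take enrollment as consent (Section 9.2), count without a Day 0, apply criterion 6 (24 hours of PPI before enrollment), and read PK Visit 2 from Figure 1.

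| Enrollment | Tube expected to at least | PPI started by | Earliest PK Visit 2 | Reached? |
|---|---|---|---|---|
| Day −3 | Day 1 | Day −4 | Day 2 | one day short |
| Day −2 | Day 2 | Day −3 | Day 2 | yes |
| Day −1 | Day 3 | Day −2 | Day 2 (Day 3 on a strict four-day PPI count) | yes |
| At first dose | Day 4 | Day −1 | Day 3 (up to Day 4 in Table 4) | yes |

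So the tube is usually expected to be available at PK Visit 2, and deferring the switch would usually be workable.

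**5. What deferral costs.** If a switch were possible from dose 2, deferral keeps doses 2–3, 2–5 or 2–7 on the tube. That is 2, 4 or 6 doses: 2/28 = 7.1%, 4/28 = 14.3% or 6/28 = 21.4% of the course.

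**6. How often.** The protocol gives no rate. Purely as an illustration, if 5% to 20% of 16 participants reaching PK Visit 2 had already switched, 16 × 0.05 = 0.8 to 16 × 0.20 = 3.2 suspension profiles would be lost. Nothing in the protocol supports any value in that range.

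**The case against.** The best reply is that this will hardly ever happen. Entry requires respiratory failure and a tube expected to stay for days. The participant must then be extubated and swallowing within about 24 to 72 hours of the first dose, and for many the relevant visit is already Day 2. The trigger also presupposes earlier intubation, which not every eligible participant will have had. All of this stands and keeps the priority low, but it does not remove the conflict between the rules.

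Three stronger readings are tempting, and the protocol does not support them.

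- *A capsule profile could count toward the 16.* The three evaluability items name no formulation, so a reader might infer this. But Section 4.1 itself describes the samples as following suspension, Section 8.5.1 refers back to Table 4, and Table 9 has the PK set defined before any analysis. The supportable consequence is a lost profile, not a miscounted one.
- *Exposure would differ.* Suspension is separated from feeding by 2 hours, whereas capsules may be taken with or without food, and with water once the PPI is stopped. Yet Section 2.2.3.5 anticipates no significant difference for capsules with cola under acid suppression (from in vitro data and modelling). The water case would rarely arise at PK Visit 2, which presupposes four consecutive days of PPI.
- *The sample size fails.* The allowance of about 25%, attributed to disease progression and applied to 20, gives 5 losses and leaves 15, which might suggest no room for early recovery. But 20 is itself approximate, Section 9.2 also cites variability in treatment duration and PPI use, and no hypothesis is tested. No shortfall is demonstrated.

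It is also fair to say that keeping a recovered participant on tube dosing is a clinical trade-off. That stands in part, and it is why the proposed wording leaves the Investigator an override.

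**Conclusion.** The point holds in a limited form. Followed exactly, Section 6.1.2.2 can forfeit the suspension profile at PK Visit 2 while the tube that would have delivered the dose is still in place, and no other section prevents it. Each occurrence costs one participant of the 16. The frequency is unknown and probably low.

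The tube-availability check rests on reading enrollment as consent and on the PK Visit 2 days in Figure 1; on a different reading of either, the match shifts by about a day.

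PK Visit 3 can also fall after a switch, since it is set by "Third PK sampling will occur 3 days after PK Visit 2, OR on the last day the participant receives acalabrutinib treatment, whichever comes first", but it does not enter the evaluability definition and needs no change here. I would rate this between optional and a low-priority recommendation: a cheap improvement that protects the primary objective, not a flaw that threatens the study.

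**What to change.** Add to Section 6.1.2.2, and align Table 5 footnote a: *If the gastric tube is still in place, the switch to capsules is deferred until the 12-hour sample of PK Visit 2 has been taken, unless the Investigator judges tube dosing clinically inappropriate; the tube is not kept in for PK sampling alone.* After that sample the present rule applies unchanged.

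For consistency, reword evaluability item (1) in Section 4.1 and the synopsis as: *complete PK Visit 2 assessments after a suspension dose given through the gastric tube.* This only makes explicit what Section 4.1 already implies. Any separate summary of capsule profiles belongs in the SAP.

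The cost is wording in four places, with no added visits, samples or procedures; Section 6.4 already has sites record suspensions and capsules taken. The downside is that some participants who could swallow stay on tube dosing for up to 2, 4 or 6 of 28 doses, with its 2-hour separation from feeding and other drugs.

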### **6.1.2.3 Missed Dosing Windows and Doses**

The bid doses should be scheduled approximately 12 hours apart. It is recommended that acalabrutinib be taken as close to the scheduled time as possible (within  $\pm 1$  hour). However, if the scheduled time is missed, it can be taken up to 3 hours after the scheduled time, with a return to the normal schedule upon the following dose for 14 days (a maximum of 28 doses).

If the 3-hour dosing window is missed, the dose must be skipped on that day. Acalabrutinib may be held for a maximum of 3 consecutive days (6 consecutive doses) from expected dose due to toxicity. If a dose is missed due to an AE or for any other reason, missed doses should be completed so the participant receives a maximum of 28 doses of acalabrutinib, even if this is beyond the 14-day dosing period.

### **6.1.2.4 Vomiting After Acalabrutinib Treatment**

If vomiting occurs after taking acalabrutinib, the participant should not retake acalabrutinib until the next scheduled dose.

### **6.1.2.5 Discharged From Hospital Before Treatment Completion**

Participants who are discharged from the hospital before they have completed 14 days (a maximum of 28 doses) of acalabrutinib therapy must complete the remaining doses at home. They should adhere to their established dosing schedule. These participants must complete a drug dosing diary to be sent electronically to the study site.

## **6.2 Preparation/Handling/Storage/Accountability of Interventions**

### **6.2.1 Preparation and Handling**

Refer to the Handling Instructions for the preparation and handling of acalabrutinib suspension in COCA-COLA delivered via NG tube to participants.

### **6.2.2 Storage and Accountability**

Acalabrutinib should be stored according to the instructions on the label affixed to the package of the drug product.

If a drug shipment arrives damaged or if there are any other drug complaints, a Product Complaint Form should be completed and emailed to the Sponsor or the Sponsor's representative. Refer to the IB for additional information regarding the drug product to be used in this study.

The Investigator or designee must confirm appropriate temperature conditions have been maintained during transit for all study intervention received and any discrepancies are reported and resolved before use of the study intervention.

Only participants enrolled in the study may receive study intervention and only authorized site staff may supply or administer study intervention. All study intervention must be stored in a secure, environmentally controlled, and monitored (manual or automated) area in accordance with the labelled storage conditions with access limited to the Investigator and authorized site staff.

The Investigator, institution, or the head of the medical institution (where applicable) is responsible for study intervention accountability, reconciliation, and record maintenance (ie, receipt, reconciliation, and final disposition records).

Further guidance and information for the final disposition of unused study interventions are provided in the Clinical Study Agreement.

## **6.3 Measures to Minimize Bias: Randomization and Blinding**

This is an open-label study and blinding is not applicable.

## **6.4 Study Intervention Compliance**

When participants are dosed at the site, they will receive study intervention directly from the Investigator or designee, under medical supervision. The date, and time if applicable, of dose administered in the clinic will be recorded in the source documents and recorded in the eCRF. The dose of study intervention and study participant identification will be confirmed at the time of dosing by a member of the study site staff other than the person administering the study intervention.

For participants who are discharged from the hospital before they have completed 14 days (a maximum of 28 doses) of acalabrutinib and must complete the remaining doses (capsules) at home, compliance with study intervention will be assessed via a drug dosing diary that must be sent electronically to the study site at each visit and documented in the source documents and eCRF. Deviation(s) from the prescribed dosage regimen should be recorded in the eCRF.

A record of the number of acalabrutinib suspensions or capsules dispensed to and taken by each participant must be maintained and reconciled with study intervention and compliance records. Intervention start and stop dates, including dates for intervention delays and/or dose reductions will also be recorded in the eCRF.

